##### **5.1.4 Stem cell lab processing of the pheresis product**

Depending on the volume of the product and the total nucleated cell count (TNC) in it, additional processing may be required to minimize volume. The recommended storage cell concentration should not exceed  $2 \times 10^8$ /mL. This will require centrifugation and plasma

reduction at 1000X G for approximately 15 minutes. The excess plasma is discarded then. The total cell count and volume of the concentrated product is determined. The proportion of the following components in the final product should be approximately: PBMC 75%, plasma/serum 5%, Plasma-Lyte 9.5%, DNase 0.5% and DMSO 10% per unit volume. For example for a 100 ml final product volume the PBMC should be 75ml, plasma/serum 5 ml, plasma-Lyte 9.5 ml, DNase 0.5 ml, and DMSO 10 ml. The product is then taken to the controlled rate freezer before final transfer to liquid nitrogen.

#### 5.1.5 Stem cell mobilization

Subjects in all groups will receive G-CSF as subcutaneous injections daily (10 µg/kg/day) x 5 days starting on day -11 (after 1st leukapheresis for groups 1). Subjects will receive one dose of plerixafor followed by pheresis on the next day to collect G-PBSC graft. No Cyclophosphamide mobilization is allowed on this protocol. Follow standard of care for stem cell collection.

#### 5.1.6 Graft processing on the experimental arm

The stem cell product may start to be washed while waiting for the CD34+ content to known. Subjects who fail to mobilize a minimum of 6 million CD34/kg on day 1 of leukapheresis will be removed from the experimental arm of the study (these subjects will be treated and followed like group 2 for a separate analysis at the end).

- Subjects who mobilize 6-10 million CD34/kg on day 1:
  - will proceed to CD34 stem cell selection on the Milteny device, provided that the TNC content does not exceed the column capacity. They will proceed to day 2 collection to complete CD34 need for second stem cell transplant 2 million CD34/kg + 2 million CD34/kg reserve for potential “boost” need in case of graft failure on protocol (hence 4 total).
- Subjects who mobilize >10 million CD34/kg on day 1:
  - They can have approximately up to 10 million CD 34/kg processed on the Miltenyi column, if the TNC content does not exceed the column capacity (remainder difference for the second AHSCT and the boost will be collected on the following day 2 of collection).
- Collecting at least 14 million CD34/kg on day 1 will complete stem cell collection process(10 for Miltenyi, 2 for second AHSCT and 2 for boost).

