**Schema:**

As shown in the schema above:

- 1- Subjects in all groups will receive tetanus vaccine 7-10 days prior to mobilization.
- 2- Subjects in group 1 will have mononuclear cells collected and frozen 7-10 days after tetanus vaccination pre-transplant. These subjects will then receive a CD34+ selected graft on day 0 and autologous donor lymphocyte infusion (DLI) on day +7.
- 3- Subjects in group 2 will receive a standard G-CSF mobilized graft on day 0 without any DLI post-transplant.
- 4- Subjects in all groups will receive G-CSF as subcutaneous injections daily (10 µg/kg) x 5 days starting on day -11 (following the DLI pheresis in the experimental group). Subjects will receive one dose of plerixafor, a stem cell mobilizer, followed by pheresis on the next day to collect G-PBSC graft, with the goal of  $> 6.0 \times 10^6$  CD34+ cells/kg.
- 5- On day of G-PBSC pheresis, the graft in group 2 will be analyzed for CD34, lymphocyte content, and T-reg and MDSCs (cell differential and flow cytometry). Then it will be processed and frozen as per local institutional standards.
- 6- The stem cell product will start to be washed while waiting for the CD34+ content to be known. CD34+ stem cells will then be selected out of the G-PBSC mobilized graft the same day using clinical grade CD34+ magnetic beads and Clinimacs device from Miltenyi as per manufacturer's instructions and as described below. The CD34 content will be analyzed before freezing in liquid nitrogen.
- 7- The subjects in all groups will receive high dose chemotherapy Melphalan at 200 mg/m^2 on day -1.

8- On day 0, subjects in group 1 will receive the thawed CD34+ stem cell graft, while subjects in the group 2 will receive the standard thawed G-PBSC graft. Transplanted CD34+ stem cell dose both groups will be in the range of 2-10 X 10^6/Kg body weight.

9- On day +7 post-transplant, the stored autologous donor lymphocyte product in group 1 will be thawed and infused back to the subjects.

10- **No planned G-CSF post-transplant** (unless medically deemed necessary due to slow engraftment by day 15)

11- Subjects will be followed closely in the hospital until engraftment and resolution of all transplant related toxicities.

12- Subjects will be closely evaluated for any trial related adverse events, specifically: delayed engraftment, auto-immune side effects (autologous graft versus host disease), and infections.

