#### **4.3 Randomization**

The protocol will randomize subjects to two subsequent arms (10 subjects per arm): group 1 will get a CD34+ selected graft + autologous DLI on day+7, while group 2 will get standard G-CSF mobilized graft only.

The process of a 1:1 randomization between the experimental and control arms. During the registration procedures, study personnel are provided the randomization assignment from the the

IIT Office project coordinator. The 1:1 randomization will be conducted using blocked randomization with blocks of size 2 or 4.

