### **5.6 Removal from the study**

Subjects who for whatever reason do not meet the cardiac ejection fraction, pulmonary function test requirement or develop significant organ dysfunction before the transplant admission will be removed from the study.

The investigator will withdraw a subject from the study treatment whenever:

1. Continued participation is no longer in the subject's best interests. Reasons for discontinuing treatment may include the occurrence of a SAE or an inter-current illness. These subjects will be taken off treatment and followed according to the study calendar.
2. The subject requests to end treatment.
3. Subjects who fail to collect a minimum of 6 million CD 34 cells/kg body weight at the end of 1st day of Leukapheresis will be either removed or transferred to arm 2 of the protocol after discussion with the PI.

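### Group 1 subjects who miss the day-1 CD34 cut leave the experimental arm after randomisation, Sections 5.1.6 and 5.6 handle them differently, and Section 10 names neither an analysis set nor a feasibility denominator

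*Combined protocol and SAP*

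**What the plan says.** **Timing.** Section 4.3: "During the registration procedures, study personnel are provided the randomization assignment". The Section 7.0 calendar also puts randomisation in the baseline column and graft pheresis at day -6 to -4. The day-1 CD34 yield is therefore known only after randomisation.

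**Section 5.1.6**, headed for the experimental arm: "Subjects who fail to mobilize a minimum of 6 million CD34/kg on day 1 of leukapheresis will be removed from the experimental arm". It adds that "these subjects will be treated and followed like group 2 for a separate analysis at the end".

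**Section 5.6**, in a list opened by "The investigator will withdraw a subject from the study treatment whenever", takes subjects below the same 6 million/kg day-1 cut and says they "will be either removed or transferred to arm 2 of the protocol after discussion with the PI". It names no arm and mentions no separate analysis.

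**Schema.** The collection target applies to all groups: "followed by pheresis on the next day to collect G-PBSC graft, with the goal of" more than 6 million CD34/kg. For controls, "the graft in group 2 will be analyzed for CD34, lymphocyte content, and T-reg and MDSCs". So a CD34 count is planned in both arms.

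**Section 10.** Section 10.1 compares the groups by Mann-Whitney test on days 30, 70, 100 and 180. No part of Section 10 says whether a group means as randomised, as treated or per protocol, and none describes the separate analysis that Section 5.1.6 promises. Feasibility is a primary objective in Section 1.1 but has no numerator or denominator in Section 10. Section 4.4 covers only data collection for subjects who receive no assigned treatment.

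**The concern.** The cut is a variable observed after randomisation, and Section 5.1.6 applies it to one arm. The retained group 1 then consists of adequate mobilisers, while group 2 keeps its poor mobilisers. If day-1 yield is related to later immune recovery, part of any difference in tetanus response comes from who was kept, not from the graft.

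Even if yield and response are unrelated, the analysed set is open. With 2 failures, the primary comparison could be run as 8 v 10 or 10 v 10. Feasibility could be reported as 80% or 100%. Neither choice is fixed before results are seen, although Section 10.5 plans each test at the 5% level.

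**Working it through.** **1. The plan's own power figure.** Inputs from Section 10.5: 10 per arm, d = 1.36, two-sided 5%, Normal data. The two-sample t-test gives 82.0%. Scaling n by the Mann-Whitney efficiency 3/π gives an effective n of 9.55 per arm. The noncentrality is then 1.36 × √(9.55/2) = 2.97 and power is 80.0%. The stated figure reproduces. The exact test (reject at U ≤ 23, true level 4.3%) has about 78% power by simulation.

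**2. The two rules side by side.**

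| | Section 5.1.6 | Section 5.6 |
|---|---|---|
| Cut | 6 million CD34/kg, day 1 | same |
| Arm | experimental | not named |
| Handling | as group 2 | removed, or transferred to arm 2 |
| Discretion | none stated | after discussion with the PI |
| Analysis | separate | not stated |

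They agree on group-2-like handling when a subject is transferred. They differ on outright removal, on discretion and on where the subject is analysed.

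**3. Spurious difference if failures are dropped from group 1 only.** Assumptions, not in the documents: failure rate p of 10-30%, and correlation ρ between yield and response of 0 to 0.5, jointly Normal. With c = Φ⁻¹(p), the retained group 1 mean shifts by ρ × φ(c)/(1 − p) SD with no treatment effect.

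| p | φ(c)/(1 − p) | ρ = 0 | ρ = 0.3 | ρ = 0.5 |
|---|---|---|---|---|
| 10% | 0.1755/0.9 = 0.195 | 0 | 0.06 | 0.10 |
| 20% | 0.2800/0.8 = 0.350 | 0 | 0.10 | 0.17 |
| 30% | 0.3477/0.7 = 0.497 | 0 | 0.15 | 0.25 |

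**4. False-positive rate.** The lowest 3 mobilisers of 10 are dropped, there is no treatment effect, and the exact Mann-Whitney test is run at 7 v 10. At ρ = 0, 0.3 and 0.5 the simulated rate is 4.3%, 5.1% and 6.5%. With only 1 or 2 dropped at ρ = 0.5 it is about 4.8% and 5.6%. Analysed as randomised it stays at 4.3-4.4%.

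**5. Feasibility with 2 failures (assumed), Clopper-Pearson 95% intervals.** All randomised to group 1: 8/10 = 80% (44% to 97%). Failures removed from the denominator: 8/8 = 100% (63% to 100%).

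**6. Power trade-off with 2 failures, d = 1.36, exact test by simulation.**
- As randomised, 10 v 10, the 2 failures assumed to get no benefit: about 53%.
- Section 5.1.6 as written, 8 v 10: about 72%.
- Same cut in both arms, each losing 2, 8 v 8: about 69%.

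With 1 or 3 failures, as-randomised power is about 66% or 40%.

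**The case against.** **Section 5.1.6 already gives an analysis rule, and much of Section 5.6 agrees with it.** This stands in part. The separate analysis is a rule, and transfer to arm 2 is the same handling as being treated like group 2. But that rule is itself the exclusion at issue, Section 10 never defines it, and outright removal has no counterpart in Section 5.1.6.

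**The exclusion may not be one-sided.** Section 5.6 names no arm, so removal could be read as reaching group 2. That is a fair point: the one-sided reading is certain only for Section 5.1.6. It is a further reason to reconcile the two.

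**The inflation is small and hypothetical.** This stands. Under the Section 5.1.6 rule the false-positive rate clearly exceeds 5% only with 2 or more failures and a correlation near 0.5, and both inputs are assumed. At zero correlation there is no bias.

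**Which analysis is primary is a choice of estimand, and as-randomised costs power in an exploratory pilot.** The loss is real (53% against 72%). But 8 v 10 buys its power by comparing differently selected groups. A supportive comparison with one cut in both arms recovers most of it (69%) without that asymmetry.

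**Two stronger readings are tempting but unsupported.** A reader might infer that transferred subjects are pooled with controls for analysis, which would raise the assumed bias to as much as 0.38 SD. No section says so: Section 5.6 is a list of reasons for withdrawal from treatment, and the only text on analysis keeps these subjects separate. A reader might also infer that the 80% power is wrong; it reproduces and needs no change.

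**Conclusion.** The point holds and should be fixed before analysis. Three parts rest on the text alone: a post-randomisation removal written for one arm, two sections that handle the same subjects differently, and a Section 10 with no analysis set or feasibility denominator.

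The size of any bias rests on assumptions. Over 10-30% failures and a correlation of 0 to 0.5 it is 0 to 0.25 SD, with a false-positive rate of 4.3% to 6.5% when 3 of 10 are dropped. The documents do not show that bias will occur. The effect on feasibility needs no correlation: 2 failures give either 8/10 or 8/8. Because the trial is an exploratory pilot and the inflation under the protocol's own rule is modest, this is a should-fix matter and does not in itself invalidate the design.

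**What to change.** 1. **Section 10, primary set.** State that the primary immune-response comparison and the progression-free survival comparison keep every subject in the randomised arm whatever graft is received. Report missing data by arm.
2. **Supportive comparison.** Apply the same day-1 CD34 cut to both arms, using the counts already planned for group 2 grafts. It stays supportive because group 1 has an additional pheresis before G-CSF ("starting on day -11 (following the DLI pheresis in the experimental group"), which might affect yield.
3. **Feasibility.** Use all subjects randomised to group 1 as the denominator. Count any failure to deliver the selected graft as a failure: missed day-1 yield, column capacity exceeded (Section 5.1.6), or final product below the stated CD34 content (Section 5.1.7).
4. **Reconcile Sections 5.1.6 and 5.6**, including whether removal applies to group 2. The clinical handling is for the investigators.

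**Cost.** Items 2 to 4 are wording and reporting from planned data. For item 1, subjects followed like group 2 under Section 5.1.6 need nothing extra. Subjects fully removed under Section 5.6 would have comparable data only if they also received the day +15 and +60 vaccines and were followed, to two years for progression-free survival; otherwise they are reported as missing. The statistical cost is the dilution of the as-randomised comparison shown in step 6 of the working.

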#### 5.1.7 Stem Cell lab processing for CD34+ selection

The PBSC pheresed graft is washed initially with PBS containing 5mM EDTA and 0.05% human albumin as per manufacture's standard operating procedure SOP. After reducing the total volume to 95 mls, the anti CD34 antibody (directly conjugated to magnetic micro beads Miltenyi) will be added and incubated for 30 minutes. The cells then washed with Max buffer and attached to Clinimax tubing set. The enriched cells will be cryopreserved with DMSO 7.5%, PBS/HAS 4%/heparin and stored in the gas phase of liquid nitrogen. CD34 content of the final product should be no less than 2 million/Kg body weight.

All subjects in the control group will have the graft absolute lymphocytes quantified (differential count). A sample of the graft will be sent to the stat hematology lab for white cell count and differential. In addition, another sample will be sent for flow cytometry for subset analysis.

### 5.1.8 Conditioning Regimen

Transplant preparative regimens: a single intravenous dose of Melphalan 200mg/m^2 on day -1 is used as the standard preparative regimen in subjects with multiple myeloma.

### 5.1.9 Day zero

The CD34 stem cells will be thawed and infused back to subjects in group 1. Subjects in group 2 will receive their unmanipulated graft as per standard procedures. The CD34 graft content should be in the range of 2-10 million/kg body weight in all groups. Subjects will receive maximal standard of care premedication excluding glucocorticoids.

#### Glucocorticoid Use

Due to lymphodepleting effect on the immune system, no steroids will be allowed from day 0 of ASCT until day+181, unless unavoidable for urgent clinical use (such as autoimmune diagnosis or adrenal insufficiency).

### 5.1.10 On day +7 post-transplant

Subjects in groups 1 will receive the stored autologous donor lymphocyte product after thawing via intravenous infusion. Subjects will receive maximal standard of care premedication excluding glucocorticoid use before donor lymphocyte infusion. No dexamethasone should be given on or after the day of DLI infusion.

#### **G-CSF post AHSCT will not be given.**

Subjects who show no rise in WBC as a sign of engraftment by day +15 post-transplant are allowed to receive G-CSF at 5 µg/kg daily until absolute neutrophil count is equal or > 500/µL.

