#### 2.4 Antigen specific immune reconstitution

Riemer et al. evaluated the antigen specific humoral immune response post AHSCT in 38 patients. He found that IgG antibody titers against measles, mumps, rubella, and polio were present in almost all patients pre-transplant and during 12 months post-transplant, indicating persistent humoral immunity. Svane et. al. evaluated the antigen specific cellular immune responses post AHSCT in breast cancer patients. Peripheral blood was collected from five breast cancer patients at serial time points in connection with chemotherapy treatment and in a follow-up period of 1 year. The frequencies of CD8 and CD4 T-cells responsive to cytomegalovirus (CMV), varicella zoster virus (VZV), and tetanus in antigen-activated whole blood were determined by flow cytometric analysis of CD69, (intra-cellular) TNF $\alpha$ , and IFN $\gamma$  expression. Mononuclear cells were labeled with PKH26 dye and the CMV, VZV, and tetanus toxoid-specific proliferation of T-cell subpopulations was analyzed by flow cytometry. In none of the patients did the treatment result in loss of overall T-cell reactivity for any of the antigens. Prior to chemotherapy 5/5 patients possessed TNF expressing T-cells specific for CMV, 4/5 for VZV, and 3/5 for tetanus. One year after stem cell transplantation all patients possessed TNF expressing T-cells specific for CMV, VZV and tetanus. The highest percentages of cytokine responding T-cells were seen after stimulation with CMV antigen. **In general, the lowest antigen specific immune reactivity (close to zero) was measured in G-CSF-mobilized blood at the time of leukapheresis.** Despite a continuously reduced CD4 to CD8 ratio after transplantation, recovery of antigen specific CD4 T-cells usually occurred prior to CD8 recovery and often to a higher level. This study demonstrated that natural as well as vaccine-induced specific immunity established prior to AHSCT can be regained after stem cell transplantation.

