### 2.7 The autologous graft is enriched with immune suppressive cells:

One of the immune suppressive cellular elements enriched in the G-PBSC grafts are regulatory T cells (T-reg). These CD4+CD25hi T-reg is a specialized subset of T-cells that act to suppress immune activation, and thereby maintain immune tolerance to self. FOXP3 is thought to be a characteristic marker for T-reg (a master transcriptional regulator in the development and function of regulatory T-cells). Seddiki et al. showed that expression of CD4+CD25+CD127low phenotype gave an accurate estimation of T-reg cell numbers and correlated well with FOXP3 expression. The bone marrow is an important reservoir for functional CD4+CD25hi T-reg. G-CSF mobilizes T reg from the bone marrow to the peripheral blood through down regulation of bone marrow CXCL12, a ligand for CXCR4 receptor expressed on the surface of T-reg. Ruttella et al. showed that *in vivo* exposure to G-CSF induced suppressor T-cells with a peculiar cytokine profile (IL-10 high, TGF- $\beta$ 1 high, IL-2 low, IL-4 low), and suppression of antigen-driven proliferation. A clinical trial evaluating the role of AHSCT in juvenile idiopathic arthritis demonstrated an accelerated recovery of CD4+CD25hi T-reg in peripheral blood post-transplant. This phenomenon correlated with the clinical quiescence of the autoimmune process. *In vitro* depletion of these T-reg from peripheral blood samples post-transplant partially corrected the T-cell dysfunctional state. Early after AHSCT, T-reg expansion occurs through homeostatic proliferation from the G-PBSC graft rather than through thymic differentiation.

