Another immune suppressive population abundant in the G-PBSC grafts is immature monocytes. Fraser et al. showed an increased proportion of CD14+ monocytes in G-PBSC grafts. Majority of these monocytes were immature, expressed low CD14, had surface bound IL-10, and induced significant T-cells suppression *in vitro*. Activation of STAT3 pathway and expression of FAS ligand are possible mechanisms of their immunosuppressive phenotype. G-CSF mobilized immature monocytes are recruited to the tumor microenvironment, where their phenotype is further modified to become myeloid suppressor cells (MDSC). These MDSCs are usually CD33+, CD11b+, HLA-DR low and CD15+-.

As mentioned above Saven et al. noticed the lowest level of antigen specific T-cell immune responses in G-PBSC grafts. The abundance of immune suppressor cells in G-PBSC grafts raises concern about their *in vivo* effect on the immune recovery post-transplant.

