### 5.1.13 Immune evaluation assays (anti-tetanus & immunophenotyping)

Assays will be performed on day +15 (+/- 3 days), +30 (+14days), day+70 (+14days), day+100 (+/-10 days), and Day 180(+/-10) post-transplant on both groups.

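### Rescue G-CSF can start on day +15, inside the day +15 (+/-3) immune-sample window, and nothing orders the draw before the dose or separates exposed samples in the T-reg, MDSC and AMC comparisons

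*Combined protocol and SAP*

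**What the plan says.** - **Rescue rule.** Section 5.1.10 says that G-CSF is not given after transplant, then makes an exception: "Subjects who show no rise in WBC as a sign of engraftment by day +15 post-transplant are allowed to receive G-CSF". Dosing runs "daily until absolute neutrophil count is equal or > 500", with no calendar limit. Item 10 of the Schema repeats the exception: "unless medically deemed necessary due to slow engraftment by day 15".
- **Sample windows.** Section 5.1.13: "Assays will be performed on day +15 (+/- 3 days), +30 (+14days". Section 5.1.2, Section 5.7.2 and Appendix B give the same day +15 window. As far as the table in Section 5.1.2 can be read, flow cytometry is the only assay marked at day +15.
- **What G-CSF does, by the protocol's account.** Section 2.7: "G-CSF mobilizes T reg from the bone marrow to the peripheral blood". The same section reports that in vivo "exposure to G-CSF induced suppressor T-cells with a peculiar cytokine profile", and that immature monocytes mobilised by G-CSF go on to become MDSC.
- **Analysis.** Secondary objective 2 in Section 1.2 is T-reg and MDSC recovery. Section 10.2 tests change in ALC, AMC and immune cells, including T-reg and MDSC, at days 15 and 30, and models them over all follow-up. It has no rule for samples taken after rescue G-CSF.
- **Recording.** Sections 11.0 and 11.1 ask for actual treatments and dated notes of doses. The forms listed in Section 14.0 include none for concomitant medication.

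**The concern.** The trial's premise is that G-CSF brings suppressor cells into the graft, and that keeping them out changes what is later seen in the blood. Section 5.7.2 predicts much lower T-reg and MDSC in the experimental arm. A day-15 sample drawn after a rescue dose partly measures the rescue drug, on the very cells that the comparison is about. The passage on glucocorticoid use, after Section 5.1.9, restricts steroids to protect the immune readouts, so drug exposure is already treated as a threat to them. Post-transplant G-CSF has no matching rule for sampling or analysis.

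At stake are the day-15 T-reg, MDSC and AMC comparisons, the ALC/AMC ratio in Section 5.7.1, and the day-30 values if dosing runs on. With 10 subjects per arm, one or two such samples carry weight. Draw order cannot be restored after the event.

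**Working it through.** **1. Overlap.** The sample window is 15 - 3 = 12 to 15 + 3 = 18, which is seven days. Rescue can start on day 15. Days 15, 16, 17 and 18 can follow a dose, so 4 of 7 days are open to exposure. If the day-15 draw always precedes that day's dose, it is 3 of 7. The day +30 window is days 30 to 44 and opens 15 days after the earliest rescue dose, so it is affected only if dosing or its effect lasts that long.

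**2. The plan's own power figure.** Section 10.5 gives 10 per arm, two-sided 5%, d = 1.36, Mann-Whitney test with a normal parent, and power of at least 80%. With effective n = 10 x 3/pi = 9.55 per arm, the noncentrality is 1.36 x sqrt(9.55/2) = 2.97 on 2 x 9.55 - 2 = 17.1 degrees of freedom, and power is 0.800. The figure reproduces. The exact test (reject at U <= 23) gives 0.78 by simulation, which is the baseline below.

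**3. Effect of exposed samples (illustration).** Assumptions: d = 1.36 is borrowed from the primary-endpoint calculation, group 1 is truly lower, and each exposed sample is raised by s SD. The documents give neither the number exposed nor s.

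| Exposed samples | s = 1 SD | s = 2 SD |
|---|---|---|
| none | 78% | 78% |
| 1 in group 1 | 70% | 60% |
| 2 in group 1 | 61% | 38% |
| 3 in group 1 | 52% | 20% |
| 2 in each arm | 72% | 58% |
| 2 in group 2 only | 86% | 88% |

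Exposure in group 1 hides a true difference, equal exposure dilutes it, and exposure in controls exaggerates it.

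**4. How likely is exposure?** Take an assumed rescue rate r in group 1 and draws spread evenly over the window. The exposure rate is q = r x 4/7, and P(at least 2 of 10) = 1 - (1 - q)^10 - 10q(1 - q)^9.

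- r = 10%: q = 0.057, and P = 1 - 0.555 - 0.336 = 0.11.
- r = 5%, 20%, 30%: P = 0.03, 0.32, 0.53.

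Averaged over the number exposed at r = 10%, with exposure in group 1 only, power is about 73% (1 SD) or 67% (2 SD), against 78%.

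**5. Could the result reverse?** The mean difference is -1.36 + ks/10 for k exposed group 1 samples, so it reaches zero at s = 13.6/k: 6.8 SD for k = 2, 4.5 SD for k = 3 and 2.7 SD for k = 5. Even with k = 5 and s = 3, a significant result in the wrong direction occurs in about 0.3% of runs.

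**The case against.** The strongest reply is that exposure will be rare and the mechanism is stretched.

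- **Rarity.** Section 2.3 has white cells recovering within two weeks. Section 5.3 calls engraftment failure unlikely with CD34-selected grafts and reports none in two earlier subjects. The trigger is narrow, and zero exposed subjects is plausible. This stands, and step 4 shows the modest average loss. However, the Schema lists delayed engraftment among the events to watch, and no rate is given.
- **Mechanism.** Sections 2.4 and 2.7 largely describe mobilised blood and grafts, and Section 2.7 places the conversion to MDSC in the tumour microenvironment. Extending this to short rescue use is an inference. Slow engraftment itself also alters day-15 counts. Both points stand.
- **Power figures.** d = 1.36 is not an effect size for these cells, and Section 10.2 names signed-rank tests on change and mixed models, not a Mann-Whitney test on levels. This stands, so the table shows sensitivity and is not a forecast.
- **Unseen documents.** The Manual of Operations and lab manual named in Section 14.0 could fix the draw order. Even so, Section 10.2 would still lack a rule for exposed samples.

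A reader might infer three stronger things. The first is that the arm difference could reverse; step 5 shows that this needs about half of group 1 exposed to a large shift. The second is that the bias must run against the experimental arm; that holds only if that arm is rescued more often, which the documents do not show. The third is that the primary endpoint is affected, because Section 2.4 reports near-zero antigen reactivity in G-CSF-mobilised blood and Section 5.1.12 gives a vaccine on day +15. But the primary comparisons start at day 30, and the Section 2.4 finding comes from five breast cancer patients at leukapheresis.

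**Conclusion.** The concern holds for secondary endpoints. As written, the plan lets rescue G-CSF precede the day +15 immune sample on up to four of its seven allowed days, and it analyses that sample as if unexposed. By the protocol's own rationale, this can bias or dilute the day-15 T-reg, MDSC and AMC comparisons, and the day-30 ones if dosing continues. The direction is unknown in advance.

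The size cannot be fixed from the documents. On the borrowed d = 1.36, one or two exposed group 1 samples at 1 to 2 SD take power from 78% to between 70% and 38%. At an assumed 10% rescue rate the average loss is about 5 to 11 points. The conclusion rests on rescue being used at least once near day 15 and on its effect resembling that of mobilisation. The case for a rule does not depend on the direction. Reversal, a certain bias against group 1, and an effect on the ELISPOT/ELISA endpoint are not supported.

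**What to change.** 1. **Sections 5.1.2 and 5.1.13.** State that, for a subject without a WBC rise, the day +15 immune sample is drawn within the existing window and before the first post-transplant G-CSF dose where possible. Say in the same sentence that rescue is neither delayed nor changed for a research draw.
2. **Case report form.** Record the draw date and time and the first and last post-transplant G-CSF dates. Section 5.7.1 takes AMC from routine counts, so also note whether the count used came before the first dose.
3. **Section 10.2.** Report G-CSF use per arm. Keep the all-sample comparison as the main one. Add a supportive analysis that sets G-CSF-exposed day-15 and day-30 samples apart, labelled as conditioning on a post-randomisation event that is linked to engraftment.

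The cost is one sentence on draw order, a few form fields and one extra analysis, with no new visit or sample. Some exposed samples will remain where the draw cannot come first, and the recorded times will identify them.
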